## 5.2 Eliciting and Reporting Adverse Events

The investigator will assess subjects for the occurrence of AEs from the time the ICF is signed until the end of the trial. For this trial, information on AEs will be followed for up to 28 days after the last dose of aripiprazole IM depot 400 mg has been administered and 56 days after the last of aripiprazole 2M LAI 960 mg has been administered. To avoid bias in eliciting AEs, subjects should be asked the following nonleading question: "How are you feeling?" All AEs (serious and nonserious) reported by the subject must be recorded on the source documents and eCRFs provided by the sponsor. Serious AE collection is to begin after a subject has signed the ICF.

Use medical terminology in AE reporting. Adverse events should be reported as a single unifying diagnosis whenever possible or, in the absence of a unifying diagnosis, as individual signs or symptoms. Exacerbation or disease progression should be reported as

Protocol 031-201-00181

AEs only if there are unusual or severe clinical features that were not present, not experienced earlier, or not expected based on the course of the condition.

In addition, the sponsor must be notified immediately by telephone, fax, or e-mail of any IREs according to the procedure outlined below in [Section 5.3](#). Special attention should be paid to recording hospitalization and concomitant medications.

### **5.3      Immediately Reportable Events**

The investigator must report any SAE, any AE related to occupational exposure, potential serious hepatotoxicity, or confirmed pregnancy immediately after either the investigator or trial site personnel become aware of the event. An IRE form should be completed and sent by fax, e-mail, or overnight courier, using the contact information on the title page of this protocol. (Please note that the IRE form is a specific form and is NOT the AE eCRF).

Subjects experiencing SAEs should be followed clinically as described in [Section 5.7.2](#). It is expected that the investigator will provide or arrange appropriate supportive care for the subject and will provide prompt updates on the subject's status to the sponsor.

### **5.4      Potential Serious Hepatotoxicity**

For a subject who experiences an elevation in aspartate aminotransferase (AST) or alanine aminotransferase (ALT) that is  $\geq 3$  times the upper limit of normal (ULN), a total bilirubin level should also be evaluated. If the total bilirubin is  $\geq 2$  times the ULN, complete an IRE form with all values listed and also report as an AE on the eCRF.

### **5.5      Pregnancy**

Females of childbearing potential are women whose menstruation has started and who are not documented as sterile (eg, have had a bilateral oophorectomy, or hysterectomy, or who have been postmenopausal for at least 12 months).

For men and FOCBP, who are sexually active, there must be a documented agreement that the subject and their partner will take effective measures (ie, 2 different approved methods of birth control or remains abstinent) to prevent pregnancy during the course of the trial and for 150 days after the last dose of IMP for a female subjects or 180 days after the last dose of IMP for a male subjects. Unless the subject is sterile (ie, women who have had a bilateral oophorectomy, have had a hysterectomy, or have been postmenopausal for at least 12 consecutive months; or men who have had a bilateral orchiectomy) or remains abstinent during the trial and for 150 days after the last dose of IMP for a female subject or 180 days after the last dose of IMP for a male subject, 2 of the following approved methods of birth control must be used: vasectomy, tubal ligation, intrauterine device, birth control pills, birth control implant, birth control depot injection, condom with

Protocol 031-201-00181

spermicide, sponge with spermicide, or occlusive cap (vaginal diaphragm or cervical/vault cap) with spermicide. Any single method of birth control, including vasectomy and tubal ligation, may fail, leading to pregnancy. The contraceptive method will be documented in the eCRF. Male subjects must also agree not to donate sperm from trial screening through 180 days after the last dose of IMP.

Before enrolling men and women in this clinical trial, investigators must review the below information about trial participation as part of the ICF process. The topics should generally include:

- General information
- Informed consent form
- Pregnancy prevention information
- Drug interactions with hormonal contraceptives
- Contraceptives in current use
- Follow-up of a reported pregnancy

Before trial enrollment, men and FOCBP must be advised of the importance of avoiding pregnancy during trial participation and the potential risk factors for an unintentional pregnancy. Subjects must sign the ICF confirming that the above-mentioned risk factors and the consequences were discussed.

A urine or serum pregnancy test for human chorionic gonadotropin will be performed on all FOCBP at screening and throughout the trial at the time points presented in the schedule of assessments ([Table 3.7-1](#) for sparse sampling and [Table 3.7-2](#) for robust sampling). If a urine test is performed and is positive, the investigator will follow-up with a confirmatory serum test.

During the trial, all FOCBP should be instructed to contact the investigator immediately if they suspect they might be pregnant (eg, missed or late menstrual cycle). Male subjects should also be instructed to contact the investigator immediately, during the trial, if their partners suspect that they might be pregnant (eg, missed or late menstrual cycle).

If a subject is suspected to be pregnant before she receives IMP, the IMP administration must be withheld until the results of serum pregnancy tests are available. If the pregnancy is confirmed, the subject must not receive the IMP and must not be enrolled in the trial. If pregnancy is suspected while the subject is taking IMP, the IMP must be withheld immediately (if reasonable, taking into consideration any potential withdrawal risks) until the result of the pregnancy test is known. If pregnancy is confirmed, the IMP will be permanently discontinued in an appropriate manner (eg, dose tapering if necessary for subject safety) and the subject will be withdrawn from the trial. Exceptions to trial

Protocol 031-201-00181

discontinuation may be considered for life-threatening conditions only after consultations with the sponsor (see the title page of this protocol for contact information).

The investigator must immediately notify the sponsor of any pregnancy associated with IMP exposure during the trial and for at least 150 days after the last dose of IMP for a female subject or 180 days after the last dose of IMP for a male subject, and record the event on the IRE form and forward it to the sponsor. The sponsor will forward the Pregnancy Surveillance Form(s) to the investigator for monitoring the outcome of the pregnancy.

Protocol-required procedures for trial discontinuation and follow-up must be performed on the subject unless contraindicated by pregnancy (eg, x-ray studies). Other appropriate pregnancy follow-up procedures should be considered if indicated. In addition, the investigator must report to the sponsor, on the Pregnancy Surveillance Form(s), follow-up information regarding the course of the pregnancy, including perinatal and neonatal outcome. Infants will be followed for a minimum of 6 months from the date of birth.

## **5.6 Procedure for Breaking the Blind**

Not applicable; this is an open-label trial.

## **5.7 Follow-up of Adverse Events**

### **5.7.1 Follow-up of Nonserious Adverse Events**

Nonserious AEs that are identified at any time during the trial must be recorded on the AE eCRF with the current status (ongoing or resolved/recovered) noted. All nonserious events (that are not IREs) that are ongoing at the last scheduled contact will be recorded as ongoing on the eCRF. For any AE having been identified throughout the trial, during data analysis, additional relevant medical history information may be requested by the sponsor to further ascertain causality (including, but not limited to, information such as risk-related behavior, family history and occupation). Subjects should be given appropriate medical treatment until the resolution of any AE.

### **5.7.2 Follow-up of Serious Adverse Events and Immediately Reportable Events**

This trial requires that subjects be actively monitored for SAEs and IREs up to 28 days after the last dose of aripiprazole IM depot 400 mg is administered and 56 days after the last dose of aripiprazole 2M LAI 960 mg is administered.

Protocol 031-201-00181

Serious AEs and nonserious IREs that are identified or ongoing at the last scheduled contact must be recorded as such on the AE eCRF page. If updated information (eg, resolved status) on SAE or IRE status becomes available after a subject's last scheduled contact (up to last in clinic visit for the entire trial), this must be reported to the sponsor and recorded on the AE eCRF page, according to the appropriate reporting procedures. The investigator will follow SAEs until the events are resolved or stabilized, or the subject is lost to follow-up or has died. Resolution means the subject has returned to the baseline state of health and stabilized means that the investigator does not expect any further improvement or worsening of the subject's condition. The investigator will continue to report any significant follow-up information to the sponsor up to the point the event has resolved or stabilized, or the subject is lost to follow-up or has died.

### **5.7.3 Follow-up and Reporting of Serious Adverse Events and Immediately Reportable Events Occurring After Last Scheduled Contact**

Any new SAEs or IREs reported to the investigator which occur after the last scheduled contact and are determined by the investigator to be reasonably associated with the use of the IMP, should be reported to the sponsor. This may include SAEs or IREs that are captured on follow-up telephone contact or at any other time point after the defined trial period. The investigator should follow SAEs or IREs identified after the defined trial period and continue to report any significant follow-up information to the sponsor until the events are resolved or stabilized, or the subject is lost to follow-up or has died.

## **6 Pharmacokinetic/Pharmacodynamic/Pharmacogenomic Analysis**

### **6.1 Pharmacokinetic Methods**

Plasma concentrations of aripiprazole and its major metabolite, dehydro-aripiprazole, will be analyzed using noncompartmental methods.

Pharmacokinetic data will be summarized using descriptive statistics (median, mean, standard deviation [SD], percent coefficient of variation [CV], minimum, and maximum) for each cohort. Pharmacokinetic data will also be presented in listings.

### **6.2 Pharmacodynamic Methods**

No pharmacodynamic endpoints are to be evaluated.

### **6.3 Pharmacokinetic/Pharmacodynamic Methods**

No PK/pharmacodynamic analysis is planned.

Protocol 031-201-00181

## 6.4 Pharmacogenomic Methods

No pharmacogenomic analysis is planned.

# 7 Statistical Analysis

## 7.1 Determination of Sample Size

To establish the similarity in primary PK variables, the lower bound of the 90% CI of the geometric means ratio (GMR) of  $C_{56}$  and  $AUC_{0-56}$  after the fourth dose of aripiprazole 2M LAI 960 mg to  $C_{28}$  after the eighth dose and the sum of  $AUC_{0-28}$  values after the seventh and eighth doses of aripiprazole IM depot 400 mg should be greater than 80%, respectively.

It is estimated that a total of at least 100 subjects (ie, 50 per group) completing the trial will have at least 80% power to ensure that the lower limit of the 90% CI of the GMR of  $C_{56}$  after the fourth dose of aripiprazole 2M LAI 960 mg (test) to  $C_{28}$  after the eighth dose of aripiprazole IM depot 400 mg (reference) is greater than 0.80, assuming that the actual GMR of concentrations is 1.0 and the CV is 46%.

Among these 100 subjects, at least 30 completers enrolled to the robust sampling schedule will provide at least 80% power to ensure that the lower limit of the 90% CI of the GMR of  $AUC_{0-56}$  of aripiprazole 2M LAI 960 mg (test) to the sum of  $AUC_{0-28}$  values of aripiprazole IM depot 400 mg (reference) after the seventh and eighth doses is greater than 0.80, assuming the actual GMR of concentrations is 1.15 and the CV is 40%.

The assumption of CV used in the sample calculation is based on the PK data in the previous multiple-dose aripiprazole IM depot PK Trial 31-11-298.

To ensure adequate power of the trial, an interim analysis may be conducted by the Interim Analysis Review Committee (IARC). The final sample size could be increased as per recommendation of the IARC and as further described in [Section 7.1.1](#).

Assuming a dropout rate of 34%, approximately 152 to 258 subjects will be enrolled to have 100 to 170 completers based on the recommendation of the proposed interim analysis.

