## **3.7 Trial Procedures**

The trial will consist of a screening period of up to 30 days and a treatment period of 169 ( $\pm 2$ ) days with a follow-up period of 56 ( $\pm 2$ ) days after administration of the final

Protocol 031-201-00181

dose for the aripiprazole 2M LAI 960 mg treatment group, or a treatment period of 197 ( $\pm 2$ ) days with a follow-up period of 28 ( $\pm 2$ ) days after administration of the final dose for the aripiprazole IM depot 400 mg treatment group. Individual participation for both treatment groups will be approximately 255 ( $\pm 2$ ) days.

Subjects will provide signed informed consent prior to performing any trial procedures. Screening procedures will be performed Day -30 to -1 to determine eligibility to participate in the trial.

Subjects who meet the inclusion criteria and do not fulfill any of the exclusion criteria will return to the trial site for check-in on Day -1 or Day 1. Predose assessments and administration of IMP will be performed on Day 1. After the predose assessments, subjects will be randomized (1:1) to receive multiple doses of either aripiprazole 2M LAI 960 mg (4 injections) or aripiprazole IM depot 400 mg (8 injections) over the course of 32 weeks. Aripiprazole 2M LAI 960 mg will be administered in 56-day ( $\pm 2$  days) intervals and aripiprazole IM depot 400 mg injections will be administered in 28-day ( $\pm 2$  days) intervals.

All visits may occur within  $\pm 2$  days of the target visit date for subjects enrolled to the sparse sampling schedule and for subjects enrolled to the robust sampling schedule after discharge from the clinical unit. All subjects must return to the clinical trial site for scheduled doses, assessments, and PK sample collections. A final visit will occur 56 ( $\pm 2$ ) days after the last dose of aripiprazole 2M LAI 960 mg or 28 ( $\pm 2$ ) days after the last dose of aripiprazole IM depot 400 mg.

Trial assessments are summarized by visit in [Table 3.7-1](#) for subjects enrolled to the sparse sampling schedule and in [Table 3.7-2](#) for subjects enrolled to the robust sampling schedule.

Protocol 031-201-00181

|   | Screening        | Check-in a | Days ± 2       |       |               |    |   |    |    |     |     |     |  |     |                   |
|---|------------------|-----------------------|----------------|-------|---------------|----|---|----|----|-----|-----|-----|--|-----|-------------------|

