### 7.1.1 Interim Analysis/Sample Size Re-estimation

An interim analysis of the PK data is planned during the trial and may be performed by an IARC on approximately 50 subjects (25 subjects per treatment group) completing the trial. In this case, completers will be defined as subjects who receive a final dose of IMP (both treatment groups) at the maximum dose. Out of the 50 subjects, approximately

Protocol 031-201-00181

14 subjects (7 subjects per treatment group) will have been enrolled to the robust sampling schedule. Subjects will continue to be enrolled into the trial until either the interim analysis is complete and recommends no sample size increase or there are enough subjects enrolled to ensure 170 completers.

If the trial is stopped due to futility (as described by the interim analysis), randomized subjects will be terminated; however, if the interim analysis stops the trial for having enough conditional power, then all randomized subjects will continue until the last observation. Subjects in screening will be discontinued and no further randomization will occur.

An alpha level of 0.001 (1-sided) is allocated to estimate the sample size during this interim analysis. The corresponding final significance level is 0.049 (1-sided).

The sample size will be re-estimated only based on the conditional power determined at the interim analysis. The adaptive designs methodology published by Chen, DeMets, and Lan (2004) will be used to increase the sample size based on an interim estimate of the treatment effect size, possibly combined with other external information, without inflating the Type I error.

All the detailed calculations and re-estimation methods will be prespecified and included in the statistical analysis plan and interim analysis plan.

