**Table 7.1.1-1      Sample Size Re-estimation**

| Endpoints   | Conditional Power | Interim Analysis Recommendation              | Outcome                             |
|---|-------------------|--|-------------------------------------|
| AUC 0-56 versus sum of AUC 0-28 values              | ≥ 80%             | No adaption to the planned sample size       | 30 completers (15 per group)        |
|   | < 80%             | Increase sample size to up to 50 completers  | Up to 50 completers (25 per group)  |
| C 56 versus C 28 after the last scheduled injection | ≥ 80%             | No adaption to the planned sample size       | 100 completers (50 per group)       |
|   | ≥ 30% and < 80%   | Increase sample size to up to 170 completers | Up to 170 completers (85 per group) |
|   | < 30%             | Stop the trial                               |                                     |

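### Does the 80% power stated for C56 overstate what the design delivers once the interim futility stop is counted?

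*Protocol*

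**What the plan says.** Protocol 7.1 gives the C56 power as a statement about completers: "at least 100 subjects (ie, 50 per group) completing the trial will have at least 80% power", with a margin of 0.80, a true GMR of 1.0 and a CV of 46%. The synopsis and SAP 4 repeat it. Protocol 7.1 then says that an interim analysis may be conducted, and refers to 7.1.1.

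Section 7.1.1 places the interim at about 25 completers per group and sets the final one-sided level at 0.049. For C56, Table 7.1.1-1 has three outcomes by conditional power:

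- 80% or more: "No adaption to the planned sample size", that is, 100 completers.
- 30% to below 80%: an increase to up to 170 completers.
- Below 30%: "Stop the trial".

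The only effect that 7.1.1 names is in its sentence on increasing the sample size, which is to be done "based on an interim estimate of the treatment effect size, possibly combined with other external information". The consequence of a futility stop is spelled out: "If the trial is stopped due to futility (as described by the interim analysis), randomized subjects will be terminated". Recruitment does not pause for the interim: "Subjects will continue to be enrolled into the trial until either the interim analysis is complete and recommends no sample size increase", or until there are enough subjects for 170 completers. If conditional power is sufficient, "then all randomized subjects will continue until the last observation". The detailed calculations are deferred to the SAP and an interim analysis plan.

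**The concern.** A futility stop can only remove power. A trial stopped at 25 per group cannot succeed, even if it would have met the criterion at 50 per group. The 80% is derived from margin, GMR, CV and 100 completers alone, so it takes no account of the stop. Protocol 7.1 introduces the interim as a safeguard for power and mentions only a possible increase. A reader could take 80% as the chance of success for the whole design.

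If the stop were frequent under the planning assumption, a product that is as good as planned could be abandoned at the interim, and the stated power would be too favourable. The readable text gives neither the stop probability nor the power under the rule.

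**Working it through.** **Inputs.** Margin 0.80, GMR 1.0, CV 46%, 50 completers per group (Protocol 7.1). Interim at 25 per group, final one-sided level 0.049, thresholds 30% and 80%, maximum 85 per group (Protocol 7.1.1 and Table 7.1.1-1).

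**The stated figure.** Log-scale SD = sqrt(ln(1 + 0.46²)) = 0.4381. Distance to the margin = ln(1/0.80) = 0.2231. Standard error at 50 per group = 0.4381 × sqrt(2/50) = 0.0876, so the noncentrality is 0.2231/0.0876 = 2.547. The noncentral t with 98 degrees of freedom gives 81.2% at one-sided 0.05 and 80.9% at 0.049. The claim of at least 80% is reproduced, and it also holds at the adjusted final level.

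**The rule on its least favourable basis.** Take conditional power at the interim estimate for 50 per group, with the interim held and the stop followed. The information fraction is 25/50 = 0.5 and the critical value is z(0.951) = 1.6546, so

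CP = Φ[(Z1/√0.5 − 1.6546)/√0.5].

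- CP < 30% means Z1 < 0.908. The interim standard error is 0.4381 × sqrt(2/25) = 0.1239, so this is an interim GMR below 0.80 × exp(0.908 × 0.1239) = 0.895.
- CP ≥ 80% means Z1 ≥ 1.591, an interim GMR of 0.974 or more.
- At GMR 1.0, Z1 has mean 0.2231/0.1239 = 1.801. Hence P(stop) = Φ(0.908 − 1.801) = 18.6%, P(no change) = Φ(1.801 − 1.591) = 58.3%, and P(increase) = 23.1%.

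Integrating final success over Z1, with the middle branch taken to 85 per group, gives 77.4%. On the same normal scale the fixed-sample power is 81.4%, so the net cost is about 4 points. Of the 18.6 points stopped, 8.2 would have passed at 50 per group; the increase to 85 recovers part of that loss. A simulation with estimated variances gives 77.2%.

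**Overrun.** Because enrolment continues during the interim, the branch with CP ≥ 80% may finish above 50 per group. Power is then 78.3%, 78.9% or 79.5% with 60, 70 or 85 per group. No enrolment rate is given, so these sizes are assumptions.

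**Other bases that the text leaves open**, with no overrun:

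| Basis | P(stop) | Power |
|---|---|---|
| 75% weight on interim estimate, 25% on GMR 1.0 | 15.4% | 80.3% |
| Interim estimate, both thresholds judged at 170 completers | 12.7% | 81.2% |
| 50% weight on interim estimate | 11.7% | 83.4% |
| Interim estimate at 100, stop not followed, trial taken to 100 | none | 85.6% |
| GMR 1.0 used throughout, increase always to 170 | 3.7% | 89.4% |

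With no overrun, power falls below 80% only if the interim estimate carries more than about 77% of the weight and conditional power is judged at 100 completers.

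**Sensitivity to the planning inputs.** On the least favourable basis with no overrun, power is 80.0% at CV 44% and 80.2% at GMR 1.01.

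**The case for a change.** The strongest case for a change runs as follows. Section 7.1.1 calls the interim planned as well as optional, and the enrolment range of 152 to 258 depends on its outcome. A single conditional-power column serves all three C56 outcomes, and the interim estimate is the only effect named, so the 77.4% basis is a natural reading. On it, a product that meets the planning assumption is stopped almost one time in five, and no later increase can lift power above 100 − 18.6 = 81.4%. The remedy would be a sentence of text.

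Part of this stands. The readable protocol and SAP do not report the rule's operating characteristics, and the 18.6% is correct on its basis. A label saying that 80% is fixed-sample power would do no harm.

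The rest does not carry a change. The effect is named in the sentence on increasing the sample size, not for the stop, and external information is expressly allowed. Zero overrun is also the slow end of what 7.1.1 implies. At 34% dropout, 50 interim completers need about 50/0.66 = 76 randomized subjects, and the last of them reaches Day 225 some 32 weeks after first dose. Staying within 152 randomized then means at most 76 more in 32 weeks, about 2.4 a week over roughly 20 sites. About (258 − 76)/32 = 5.7 a week would reach 258. At that end the shortfall from 80% is half a point.

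**Conclusion.** The concern does not hold as a fault in the plan. The quoted sentence is conditional on 100 subjects completing, and it is correct at 81.2% (80.9% at the final level of 0.049). A shortfall of 0.5 to 2.6 points below 80% needs four things together: an interim that is held, a stop that is followed, conditional power judged at 100 completers, and nearly all the weight on the interim estimate. The readable text settles none of these. It assigns the detail to the SAP, which is partly redacted, and to an interim analysis plan that is not among the documents, so the detail cannot be called absent from the plan.

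The shortfall is also no larger than the effect of moving the CV by 2 percentage points or the GMR by 0.01. The stop is a fair trade-off: it bears on the sponsor's chance of success and does not weaken a positive result. At a true GMR of 0.80, the same rule on the interim-estimate basis with no overrun meets the criterion 3.6% of the time, against the nominal 4.9%.

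Reporting the stop probability next to the 80% would be a courtesy to the reader. It would alter no sample size, decision rule, analysis or conclusion. All figures treat the normal-scale calculation as adequate, cover C56 only, and do not use the interim alpha of 0.001 as an efficacy stop.
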